2.3.14.2. Statistical methods for additional analysis

For the primary and secondary outcomes, logistic regression analyses will be conducted to test a difference in rates of errors between urban EMS (defined as a primary EMS agency in a area populated with 50,000 or more people in the immediate proximity of a tertiary care PED)⁵⁶ and rural EMS (i.e. EMS agency not included within an urban area) with PedAMINES and with the conventional preparation method. In a GEE logistic regression model, an interaction between interventions and urban/rural EMS will be tested to investigate a potential modification of the efficacy of PedAMINES in rural area compared with urban area. Results will also be correlated to the EMS exposition (i.e. total number of emergency calls per year per EMS divided by the number of paramedics working in that EMS). Analyses of primary and secondary outcomes will be conducted in paramedics with more or less than 10 years of experience.

Means and standard deviations will be determined for stress and satisfaction scores (Likert scale) of individuals for each questionnaire item as well as for the UTAUT questionnaire and reported with descriptive statistics. Pearson correlations will be computed between the HR measures obtained with the watch and the scenario phases for each of the drugs and preparation methods used.

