2.3.3. Study design

The study is a prospective, multicenter, randomized controlled trial with 2 parallel groups comparing PedAMINES^{46,47} with conventional precalculated drug dosing charts used by EMS in the preparation of direct IV drugs during a standardized simulation-based pediatric cardiac arrest scenario. The drug dosing charts is presented as a spreadsheet, enabling the preparation of the commonly ordered concentrations of emergency medications at varying dose ranges based on the patient's weight. To calculate the composition of the drug to inject, one first selects the desired drug dosage to be delivered in mg/kg. The next step is to calculate the milliliters of drug based on the weight of the patient to be diluted with compatible fluids (sodium chloride 0.9%, etc) in a syringe. For the purpose of the study, we will not select drugs that can be directly drawn from the vial without calculation and dilution.

The multicentric setting of the study will involve 15 Swiss EMS (Cantons of Geneva, Vaud, Neuchâtel, Fribourg, Jura, Zurich, Bern, Basel, Lucern, Ticino). To ensure optimal quality of reporting, the trial is formatted according to the Consolidated Standards of Reporting Trials Statement for Randomized Controlled Trials of Electronic and Mobile Health Applications and Online TeleHealth (CONSORT-EHEALTH)⁴⁸ and the Reporting Guidelines for Health Care Simulation Research⁴⁹

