2.3.5.4. Concomitant care

The paramedics will be allowed to use their current, conventional method of preparing direct IV drugs, even if it differs between EMS. This will avoid introducing evaluation bias on the baseline ability of paramedic to prepare drugs “as usual” if allocated in the group without PedAMINES. This will also test the absolute capacity of the app to reduce medication errors and drugs delays, indifferently of the prior traditional method used.

However, participants will not be allowed to use any other drug support device and the scenario will remain secret until it starts to avoid upstream drugs preparation's refresh.

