2.3.8. Sample size

The primary objective of this study is to detect a difference in proportions of medication errors between groups (with PedAMINES vs without PedAMINES). The expected proportion of errors made without PedAMINES is 60%¹¹. We consider that a difference of 30% in the proportion of medication errors is sufficient to modify the practice. Therefore, the sample size was calculated to reach a statistical power of 90% in detecting an absolute difference of at least 30% in proportions of medication errors between intervention groups. With a two-sided risk alpha of 0.05, the needed sample size is 56 paramedics per arm of the study. To prevent a potential loss of power due to misspecification of assumptions, 60 paramedics will be recruited per randomized group (total sample size: 120 paramedics).

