2.3.14. Statistical methods

2.3.14.1. Statistical method for primary and secondary outcomes

Primary outcome: proportion of medication errors

The proportion of medication errors is the proportion of paramedics committing a medication error. For each type of medication (epinephrine, midazolam, dextrose 10%, sodium bicarbonate), the proportion of medication errors will be reported with 95% confidence intervals (CI, Clopper-Pearson's method) when PedAMINES is used and when the conventional preparation method is used. The difference in proportion of medication errors between preparation methods will also be reported with 95% CI (exact method). The association between the preparation methods (PedAMINES versus conventional method) and the risk of error will be assessed by using a logistic regression model with mixed effects to account for the repetition of measures among paramedics. A random intercept will be introduced in the model. The model will be adjusted for the type of medication since the risk of error can vary across medications.

Secondary outcomes:

a) Proportion of other errors:

The proportions for other types of errors (the choice of drug, air purge in the syringe, labeling of the filled syringe, aseptic errors) will be analyzed in a similar manner as for the primary outcome.

b) Deviation from the correct weight-based dose:

For each of the 4 drugs prepared, errors will be measured by the deviation from the amount of drug taken, the amount of saline solution taken to dilute the drug, the final concentration and the correct weight-based dose. Absolute deviation will be analyzed for each type of medication. The mean (or median) difference in deviation obtained with PedAMINES and with the conventional preparation method will be reported with 95% CI (or inter-quartile interval). A t-test or a Mann-Whitney's test will be used for comparing preparation methods.

c) Time to drug preparation (TDP) and delivery (TDD):

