For TDD and TDP, the mean times will be reported with 95% CI for each preparation methods and for each type of medication. The mean difference between preparation methods will also be reported with 95% CI. The association between the preparation methods and TDP and TDD will be assessed by using a linear regression model with mixed effects to account for the repetition of measures among paramedics. A random intercept will be introduced in the model. The model will be adjusted for the type of medication since TDP and TDD can vary across medications.

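### The by-arm urban/rural comparison tests an agency-level factor carried by 15 EMS, but the plan names no EMS term or cluster

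*Combined protocol and SAP*

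**What the plan says.** Section 2.3.14.2 (additional analysis) plans that "logistic regression analyses will be conducted to test a difference in rates of errors between urban EMS" and rural EMS, by preparation method. It defines urban and rural for the agency, by population and proximity to a tertiary pediatric emergency department, so all paramedics of one agency share the same value. On the number of agencies, section 2.3.3 says: "The multicentric setting of the study will involve 15 Swiss EMS".

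Two related analyses follow in section 2.3.14.2. One is a test of effect modification: "In a GEE logistic regression model, an interaction between interventions and urban/rural EMS will be tested". No cluster unit is given for that GEE. The other concerns call volume per paramedic: "Results will also be correlated to the EMS exposition". No test or unit is given.

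Elsewhere in section 2.3.14 the only dependence handled is that of repeated drugs within a paramedic. The main error model is a "logistic regression model with mixed effects to account for the repetition of measures among paramedics", and the model for preparation and delivery times is a "linear regression model with mixed effects to account for the repetition of measures among paramedics". EMS is a randomization stratum (section 2.3.10.1) but appears as a random effect or cluster in no model. Section 2.3.5.4 adds: "The paramedics will be allowed to use their current, conventional method of preparing direct IV drugs, even if it differs between EMS".

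**The concern.** A factor that is constant within an agency can only be compared between agencies. Its standard error must therefore include the variation between agencies. Neither a plain logistic model nor one that accounts only for repeated drugs within a paramedic does this. Both treat the roughly 60 paramedics of an arm (or their 240 preparations) as independent evidence on a contrast that rests on 15 agencies.

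If agencies differ, intervals are too narrow and chance differences between a few agencies can be reported as an urban/rural difference. The documents give a reason to expect such variation in the conventional arm, because local methods may differ. They give no such reason for the PedAMINES arm. The summary foresees a benefit in remote places with little pediatric exposure, so a spurious by-arm difference might be cited in support.

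**Working it through.** **The plan's own figure.** No figure is given for the urban/rural comparison. The primary sample size in section 2.3.8 uses 60% errors without the app ("The expected proportion of errors made without PedAMINES is 60"%), a 30-point difference, two-sided alpha 0.05 and 90% power:

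n = [1.96 × √(2 × 0.45 × 0.55) + 1.2816 × √(0.24 + 0.21)]² / 0.30² = (1.379 + 0.860)² / 0.09 ≈ 55.7, so 56 per arm.

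This reproduces. It concerns the randomized comparison only.

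**Inputs.** From the documents: 15 EMS; 60 paramedics per arm, so 60/15 = 4 per EMS per arm on average; 4 drugs each; 60% errors in the conventional arm; 30% (60 minus 30) or about 10% (10.2% in the in-hospital crossover trial, section 2.2) with the app. Assumed, because the documents do not state them: the between-EMS SD, a paramedic SD of 1 on the logit scale, equal EMS sizes, and an urban/rural split of 8/7 (4/11 as a variant).

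**Closed-form check.** With one result per paramedic, the design effect is DE = 1 + (4 − 1) × ICC, and the true size of a nominal 5% test is 2 × [1 − Φ(1.96/√DE)].

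- ICC 0.05: DE 1.15, size 6.8%
- ICC 0.10: DE 1.30, size 8.6%
- ICC 0.20: DE 1.60, size 12.1%

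With all 4 drugs, a within-paramedic correlation of 0.2 and clustering on paramedic only, the uncaptured variance ratio is (1 + 3 × 0.2 + 12 × ICC) / (1 + 3 × 0.2).

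- ICC 0.05: 2.2/1.6 = 1.375, size 9.5%
- ICC 0.10: 2.8/1.6 = 1.75, size 13.8%

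**Simulation, conventional arm, no true urban effect, 8/7 split.** EMS SDs of 0 / 0.2 / 0.5 / 1.0 on the logit scale correspond to latent ICCs of SD²/(SD² + 1 + 3.29) = 0 / 0.01 / 0.06 / 0.19. Type I error in percent:

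| Analysis | SD 0 | 0.2 | 0.5 | 1.0 |
|---|---|---|---|---|
| Logistic, all preparations, no clustering | 11 | 13 | 18 | 29 |
| Clustered on paramedic | 6 | 6 | 9 | 17 |
| Paramedic random intercept | 6 | 6 | 9 | 16 |
| One drug at a time | 5 | 6 | 7 | 10 |
| Clustered on EMS, uncorrected | about 9 | about 9 | about 9 | about 9 |

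The t-test on 15 EMS error rates gives 4.7–5.2% throughout. Runs were 20,000 per setting, except 1,500 for the random-intercept model (Monte Carlo standard error 0.6–1.0 points). Repeat runs of the paramedic-clustered test gave 5.4–5.5 / 5.9–6.5 / 9.2–9.8 / 16.2–16.8%. With a 4/11 split, paramedic clustering gives 6 / 7 / 10 / 17% and uncorrected EMS clustering 12%.

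**PedAMINES arm.** At EMS SD 0.25, paramedic clustering gives 6.2–6.4% at error rates of 10% or 30%.

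**Call-volume correlation.** 5 / 6 / 8 / 16% if run on paramedic values; 4.7–5.2% on 15 EMS values.

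**Interaction (60% vs 30%).**

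- Clustered on paramedic, EMS effects shared by both arms: 3–5%, not inflated.
- Clustered on paramedic, conventional-arm SD 0.5–1.0 and app SD 0.25: 5–8% if EMS effects are fully correlated between arms, 8–12% if independent.
- Clustered on EMS without correction: 9–10% (12–13% with a 4/11 split).
- t-test on EMS-level arm differences: 4.7–5.3%.

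**The case against.** The strongest reply has five parts.

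- **Relevance.** The benefit foreseen in remote places concerns the app's effect, which the plan assigns to the interaction test. A by-arm difference in error rates does not test it. This stands: the link to remote benefit is only a possible misreading of the results, and the interaction is inflated only under further conditions.
- **Size.** The larger figures need a between-EMS SD that the documents do not support with data. The scenario, manikin, stated weight and study team are fixed, which limits differences between agencies. Section 2.3.14.1 also defines the outcome per paramedic and drug, and on that reading the error is only 5 / 6 / 7 / 10%. This stands as a limit on magnitude. However, plain logistic regression on all preparations is also a literal reading of section 2.3.14.2, and it is worse (11–29%).
- **Silence.** The GEE might be meant to cluster on EMS. But it is tied to the interaction, its unit is unnamed, and uncorrected clustering on 15 units is itself too liberal.
- **EMS sizes.** These are unknown. In a check with unequal sizes, paramedic clustering gave 9–13% at SD 0.5, and the unweighted EMS-level t-test rose to about 6% when urban agencies were larger. The remedy stays close to nominal.
- **Status.** The analysis is already headed as additional. That lowers the stakes, but a significance test is still planned.

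**Conclusion.** The concern holds. Followed as written, the by-arm urban/rural test ignores the level at which its factor varies, and it is anti-conservative if agencies differ. In the conventional arm, with paramedic clustering, the error is near nominal for an EMS SD up to 0.2, about 9% at 0.5 and about 17% at 1.0. These are ranges under an assumed variance, split and EMS size, not estimates. Little inflation is shown for the PedAMINES arm at a small EMS SD. The call-volume correlation shares the problem only if run on paramedic values. The interaction shares it only if the app's effect varies between agencies or if EMS clustering is left uncorrected.

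The harm is confined to additional analyses. Randomization is stratified on EMS, so the PedAMINES versus conventional comparison and its sample size are untouched. The point should be corrected before analysis, but it does not threaten the trial's main conclusion.

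**What to change.** In section 2.3.14.2:

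- State that the EMS is the unit for urban/rural and call-volume analyses, give the number of urban and rural agencies, and label the results exploratory.
- Compare EMS-level error rates between urban and rural agencies, by preparation method, with a t-test on 13 degrees of freedom. Alternatively, cluster on EMS with a Mancl-DeRouen variance and a t reference on 13 degrees of freedom. That gives a type I error of 3.3–3.6% with an 8/7 split, somewhat conservative, and 4.6–4.8% with 4/11.
- Compute the call-volume correlation on the 15 EMS values.
- Test the interaction on EMS-level differences between arms (13 degrees of freedom), or name EMS as the GEE cluster with the same correction.

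The change costs wording and code only. The downside is precision. In the conventional arm, the mean 95% half-width of the urban–rural difference goes from about 15 / 16 / 16 percentage points (clustered on paramedic) to about 17 / 19 / 25 (EMS level) at EMS SD 0.2 / 0.5 / 1.0. The difference detectable with 80% power is (2.160 + 0.870)/2.160 × half-width, or about 24 / 27 / 35 points. The plan should say that only large urban/rural differences can be shown with 15 agencies.

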2.3.6. Outcomes

Primary outcome measures: The primary outcome will be to measure, in each allocation group, the number of medication dosing errors committed during each drug preparation sequence until injection. According to Marcin et al. and Moreira et al, we defined a emergency medication dose administration error as more than 10% deviation from the correct weight dose^{9,12}.

Secondary outcome measures: The secondary outcomes will be to measure, in each allocation group, the followings variables:

A) *Errors that might be encountered during drug preparation*, such as: 1) the amount of drug taken in mL and deviation from the one prescribed on the drug dosing charts or the app, 2) the amount in mL of saline solution taken to dilute the drug, and deviation from the one prescribed, 3) final drug concentration in mg/ml obtained and deviation from the one prescribed, 4) correct or wrong drug chosen by the paramedics compared to the one prescribed on the drug dosing charts or the app (the drugs chosen will be recorded for every participant in order to find any systematic or repetitive error), 5) correct or wrong air purge out of the syringe before injection, 6) correct or wrong labeling of the filled syringe, 7) detection or not of error(s) by the paramedics, 8) stage of error(s) detection: before or after injection, and 9) aseptic errors. These measures of medication errors were selected as they were considered to be the most common sources of medication errors as evidenced in the pediatric medication error literature and meta-analysis^{17,51,52}.

B) *The time points of the drug preparation, in each allocation group*, such as: 1) time in seconds between the end of the drug prescription by the physician and the syringe filled with the drug (TDP), 2) TDP plus time in seconds between TDP and injection (TDD). TDP and TDD are relevant temporal values described in the resuscitation literature^{39,53}.

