C) *Questionnaires*: at the end of the scenario, a 6-item questionnaire using a 10-point Likert scale (scored from one to ten to avoid neutral answers) will be provided to the participants. The questionnaire measures (1) the overall stress perceived, (2) the stress perceived during each drug preparation sequence with PedAMINES and with the conventional method(s), and (3) the satisfaction about the preparation method used during the resuscitation scenario. Acceptability and usability testing of the app will be assessed using a 52-item questionnaire based on the unified theory of acceptance and use of technology (UTAUT) model⁵⁴. UTAUT provides a useful tool to assess the likelihood of success for new technology introductions and helps to understand the drivers of its acceptance.

D) *Heart rate (HR) as a stress marker*: a baseline HR before the beginning of the scenario as well as continuous HR monitoring of each participant reflecting his or her stress level will be recorded during the scenario. Mean delta HR values (difference between HR peak values and baseline HR) will be obtained during some small segments of scenario and correlated to the scenario phases and the preparation methods used.

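### Heart-rate change has no planned arm difference in bpm with a CI, and on the median route the dose-deviation difference gets an inter-quartile interval instead of a CI

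*Combined protocol and SAP*

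**What the plan says.** **Heart rate.** The Outcomes paragraph of section 1 names measured stress as a secondary outcome. Section 2.3.6 opens its list with "The secondary outcomes will be to measure, in each allocation group, the followings variables" and defines item D: "Mean delta HR values (difference between HR peak values and baseline HR) will be obtained during some small segments of scenario". It adds that these values will be "correlated to the scenario phases and the preparation methods used". The statistics are in section 2.3.14.2: "Pearson correlations will be computed between the HR measures obtained with the watch and the scenario phases for each of the drugs and preparation methods". Nothing else is planned for HR.

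**Baseline HR.** Section 2.3.6 calls it "a baseline HR before the beginning of the scenario". Section 2.3.5.1 has the watch switched on as the untimed part of the simulation begins.

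**Dose deviation.** Reducing dosing deviations is a secondary objective in section 2.3.2. Section 2.3.14.1 b) states: "The mean (or median) difference in deviation obtained with PedAMINES and with the conventional preparation method will be reported with 95% CI (or inter-quartile interval". It continues: "A t-test or a Mann-Whitney's test will be used for comparing preparation methods".

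**Comparison within the plan.** For time to drug preparation and delivery (TDP and TDD), section 2.3.14.1 c) states: "The mean difference between preparation methods will also be reported with 95% CI". It adds a linear mixed model with a random intercept, adjusted for drug. Section 2.3.14.1 also gives the difference in error proportions a 95% CI.

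**The concern.** A secondary outcome measured in both arms of a randomized trial should yield an estimate of the arm difference and its precision. The plan does this for errors and times, but not for HR or for the median route of dose deviation.

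For HR, scenario phase is a category, so a Pearson coefficient needs numeric codes that the plan does not give. A coefficient computed within one method also says nothing about whether HR is lower with the app. Readers would not learn by how many bpm the app changes measured stress, or how precisely that is known.

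It is also unclear whether baseline HR is taken before the participant knows the arm. If knowing the arm shifts baseline HR, the shift passes one-for-one, with opposite sign, into peak minus baseline.

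For dose deviation, an inter-quartile interval does not narrow as the sample grows. On that route a named objective would be reported without a usable measure of precision.

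**Working it through.** The plan states no number on this point. The only planned figure used is 60 paramedics per arm (section 2.3.8). The documents give no HR standard deviation (SD), within-paramedic correlation or distribution of deviations, so those below are assumptions.

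**1. A phase correlation depends on the coding.** Assume mean HR changes of 28, 40, 30 and 26 bpm in four equally weighted phases, with SD 15 within phase. The grand mean is 31 and the variance of the phase means is (9 + 81 + 1 + 25)/4 = 29. The total SD is √(29 + 225) = 15.94. With r = cov(code, phase mean)/(SD of code × 15.94):

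- Codes 1, 2, 3, 4: cov = −2.00, SD of code = 1.118, r = −2.00/17.82 = **−0.11**.
- Codes 0, 1, 1, 1 (arrest versus afterwards): cov = 0.75, SD of code = 0.433, r = 0.75/6.90 = **+0.11**.

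The same data give opposite signs.

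**2. A phase correlation within one method misses a uniform shift.** Replacing HR by HR − c leaves the covariance with the code and the SD unchanged, so r is the same for any c.

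**3. A correlation with arm does not give bpm.** For two equal arms, r = d/√(d² + 4), where d = difference/SD. A difference of 5 bpm at SD 10 and one of 10 bpm at SD 20 both have d = 0.5, so r = 0.5/√4.25 = 0.243 in each case.

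**4. An arm difference in bpm can be estimated.** Averaging four phases per paramedic, with within-paramedic correlation ρ, the 95% half-width is t(0.975, 118) × √[(2/60) × SD² × (ρ + (1 − ρ)/4)], with t = 1.980.

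- SD 10, ρ = 0.5: 1.980 × √(0.0333 × 100 × 0.625) = **2.9 bpm**.
- SD 20, ρ = 0.8: 1.980 × √(0.0333 × 400 × 0.85) = **6.7 bpm**.

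With a single value per paramedic, the half-widths are 3.6 bpm at SD 10 and 7.2 bpm at SD 20.

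**5. Baseline timing.** Section 2.3.7 has the scenario start straight after randomization, and section 2.3.11.1 unblinds participants after randomization. Section 2.3.10.2 withholds the allocation up to the start of the scenario. Section 2.3.5.1 puts the five-minute training after allocation, whereas section 2.3.7 puts it before. The passages allow a baseline reading on either side of the participant learning the arm.

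**6. An inter-quartile interval is not a precision interval.** For normal data with equal SD, the inter-quartile interval of between-arm differences is 2 × 0.6745 × √2 = 1.91 SD wide at any n. The 95% CI for the mean difference is 2 × 1.96 × √(2/n) SD wide: 0.72 at n = 60 and 0.36 at n = 240.

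A more realistic case assumes half-normal absolute deviations of scale 10% (app) and 40% (control), with 70% and 25% exact zeros. The figures below come from 2,000 simulated trials at 60 per arm and 300 at 240, with 1,000 bootstrap resamples each.

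| | 60 per arm | 240 per arm |
|---|---|---|
| Control-arm inter-quartile width (points) | 36.4 | 37.8 |
| Bootstrap 95% CI width, difference in medians (points) | 18.1 | 9.2 |
| Bootstrap coverage | 94.9% | 94.3% |

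Quadrupling the sample halves the CI and leaves the inter-quartile width almost unchanged.

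**7. Which interval to use instead.** Over eight assumed scenarios at 60 per arm, percentile-bootstrap coverage was 93.9–96.2%. Hodges-Lehmann coverage was 89.9–95.2% for its own parameter and 69.5–95.2% for the difference in medians. With more than half of both arms at zero (70%/55% and 90%/60%), bootstrap coverage was 99.7% and 100%, and the interval shrank to a single point in 8.9% and 31.8% of trials.

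**The case against.** HR may be meant as description only. Stress appears in no objective or hypothesis, its analysis sits under additional analyses, and perceived stress gets only means and SDs. The correlation with preparation method could test for an arm effect, so steps 1 and 2 do not show that the comparison is lost. These points are fair, and what remains is a gap in effect-size reporting. But measured stress is listed as a secondary outcome, and even a descriptive report should give the difference in bpm.

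On baseline timing, sections 2.3.6 and 2.3.10.2 together allow a reading before allocation is known. That is so, but they do not require one, and the conflicting order of training and allocation adds to the doubt.

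On dose deviation, the wording may be shorthand for per-arm medians with inter-quartile ranges. The mean route has a proper 95% CI, Mann-Whitney would still test the arm effect, and per-drug error proportions have their own interval. All of that stands. Under the shorthand reading, however, the median difference has no interval at all.

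The simulated figures rest on assumptions, and those in step 7 compare two replacements that the plan does not propose. They guide the choice of fix; the fault is in the text and does not depend on them. Zeros in more than half of both arms would also cap the control error rate at 40–45% in those two cases, below the 60% of section 2.3.8, although a single drug could differ.

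**Conclusion.** The concern holds in both parts. As written, the plan gives no arm difference in HR change with a CI. On the median route it gives no valid precision for the dose-deviation difference, and no rule says when that route applies.

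Importance is low to moderate. Both are secondary outcomes, the mean route and the Mann-Whitney test remain valid, and the primary analysis and sample size are untouched. The change is worth making because it is cheap and brings these outcomes up to the standard that the plan sets for times and error proportions.

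**What to change.** **Heart rate**
- Name the HR segments in advance; section 2.3.6 leaves them open.
- Fit the linear mixed model already planned for TDP and TDD: arm, drug phase as a factor, random paramedic intercept. Report the arm difference in bpm with its 95% CI. The correlations can stay as description.
- Record baseline HR before allocation is revealed, and reconcile the sections on the order of training, allocation and scenario. Only with a pre-allocation baseline should baseline HR also enter as a covariate.

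**Dose deviation**
- Fix the route and test in advance, for example Mann-Whitney plus the difference in medians for all four drugs.
- Report the difference in medians per drug with a percentile-bootstrap 95% CI, and keep inter-quartile ranges as per-arm description.
- If a Hodges-Lehmann shift is preferred, state that it is a different quantity and that its coverage falls with unequal spread and ties at zero.
- If more than half of both arms have zero deviation for a drug, say so and rely on the error proportions already planned.

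**Cost.** A few lines of SAP text and a little code. The one change in conduct is the timing of the baseline HR reading. The sample size does not change.

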Outcomes: the primary outcome is to measure the absolute number and the rate of medication dosage errors committed during drugs preparation sequences until injection in each allocation group. The secondary outcomes are the delays in seconds to TDP and TDD in each drug completion sequence, as well as other medication errors, perceived and measured stress. Acceptability and usability testing of the app will be assessed using a 52-item questionnaire based on the unified theory of acceptance and use of technology (UTAUT) model.

Perspectives: PedAMINES might help EMS with different competencies to prepare and deliver complicated drugs. This suggests a worthwhile benefit to its use in remote places where paramedics are little exposed to pediatric resuscitation but have to use resuscitative drugs before to transfer the patient to a tertiary care center. Being able to assess PedAMINES in the prehospital setting would be the next step to demonstrate its usefulness in multiple settings before to deploy the application all over Switzerland in real situations. It will also standardize and unify drugs prescription in Switzerland during the whole pre- and in-hospital resuscitation process. Finally, our project will also be beneficial to clinical research in Switzerland by offering a common base for further studies on prehospital medication errors.

2. Research plan

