2.3.10. Assignment of intervention

2.3.10.1. Allocation sequence

A single randomization of the participants (paramedics) will be done using an online computing web randomisation service⁵⁵ to generate the randomisation list. With this method, paramedics will be randomly assigned to either group A (using PedAMINES) or to group B (conventional preparation methods) with a single, constant 1:1 allocation ratio. One randomization list per EMS center will be produced (randomization stratified on center) and block of random size will be used to generate the randomization lists.

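### Measured stress is a listed secondary outcome, but its only planned analysis is a Pearson correlation of heart rate with scenario phases, which gives no between-arm difference in beats per minute

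*Combined protocol and SAP*

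**What the plan says.** The Outcomes paragraph of the Summary lists measured stress among the secondary outcomes: "as well as other medication errors, perceived and measured stress". Section 2.3.6, item D, defines the measure as delta HR, the peak minus a baseline taken before the scenario. It says that mean delta values "will be obtained during some small segments of scenario and correlated to the scenario phases and the preparation methods used".

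Section 2.3.14.2 gives the only statistical method for HR: "Pearson correlations will be computed between the HR measures obtained with the watch and the scenario phases for each of the drugs". The sentence goes on to add the preparation methods to the drugs.

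The two sections differ. In 2.3.6 the preparation method is one of the variables that HR is correlated with. In 2.3.14.2 the more natural reading is that HR is correlated with phase, separately for each drug and each method. Neither section defines the segments, gives the phases a numeric code, or says how several readings from one paramedic are handled.

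Section 2.3.14.1 treats the other repeated outcomes differently. Dosing errors, other errors, TDP and TDD each get a mixed model with a random intercept for paramedic, and dose deviation gets a two-sample comparison.

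**The concern.** The trial asks whether the app changes what paramedics do and experience. For HR, that question calls for a difference between arms, in bpm, with a confidence interval. The plan provides none.

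A Pearson coefficient needs two numeric variables. Scenario phase is a category, so its coefficient depends on a code that the plan does not state, and it picks up only the part of the phase pattern that is linear in that code. Phase is also repeated within a paramedic, and a simple correlation ignores this. If HR is instead correlated with method, the result is a unitless coefficient, and its validity depends on whether one value or several per paramedic enter.

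At stake is whether a listed secondary outcome has a usable planned analysis, or whether the code, the unit of analysis and the contrast are chosen after the data are seen.

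**Working it through.** **Inputs from the document.** Two parallel groups (section 2.3.3), randomised "with a single, constant 1:1 allocation ratio" (section 2.3.10.1), 60 per arm (section 2.3.8), four drugs per paramedic in a fixed order (section 2.3.5.1). The document gives no HR means, SDs or within-paramedic correlation, so those below are assumptions. I take the four drug sequences as the phases, with one segment each.

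**1. The plan's own figure.** The only design figure is for the primary outcome: "statistical power of 90% in detecting an absolute difference of at least 30% in proportions of medication errors". For 60% against 30%, with the pooled-variance formula:

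n = [1.96·√(2·0.45·0.55) + 1.2816·√(0.6·0.4 + 0.3·0.7)]² / 0.30² = (1.379 + 0.860)² / 0.09 = 55.7, so 56 per arm.

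This reproduces the stated 56. It has no bearing on HR.

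**2. HR against phase.** With code x, phase means m, and between- and within-paramedic SDs s_b and s_w:

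r = cov(x, m) / √[var(x)·(var(m) + s_b² + s_w²)]

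- Means 45, 25, 35, 20 bpm; SDs 12 and 9. var(m) = 92.2 and total variance = 92.2 + 144 + 81 = 317.2. Under the chronological code 1 to 4, cov = −8.125 and var(x) = 1.25, so r = −8.125 / √(1.25·317.2) = −0.41. Over all 24 codes r runs from −0.53 to +0.53.
- Means 30, 22, 15, 20 bpm; SDs 12 and 8. Chronological r = −4.625 / √(1.25·237.2) = −0.27, and the range over all codes is −0.34 to +0.34.
- The same means with SDs 6 and 6 give ±0.52 over all codes; with SDs 15 and 5, ±0.31.

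If the phases are the drug sequences themselves, a correlation computed within one drug has no variation in phase and is undefined. Finer phases would have to be defined first.

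**3. Can correlations within each method show an arm effect?** Adding a constant to every reading in one arm changes neither the covariance nor the variances, so r stays the same. In a simulation with the second set of inputs, a 5 bpm shift of one arm moved its mean from 21.7 to 16.8 bpm, while r was −0.269 without the shift and −0.270 with it.

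**4. HR against method, one value per paramedic.** Method has two levels, so r is the point-biserial coefficient, r = d/√(d² + 4) for a standardised difference d with equal arms. For d = 0.5, r = 0.24. In one simulated trial of 60 per arm, r was 0.228 under both codings tried, and its p-value equalled that of the t-test (0.0122 for both). This is a valid arm contrast, but not in bpm.

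**5. HR against method, four segments pooled.** The design effect is 1 + 3·ICC, so the true type I error of a nominal 5% test is 2·[1 − Φ(1.96/√(1 + 3·ICC))].

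| Assumed ICC | Type I error |
|---|---|
| 0.4 | 18.6% |
| 0.6 | 24.1% |
| 0.8 | 28.8% |

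Simulation over ICC 0.3 to 0.9 gave about 15% to 32%.

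**6. What a direct arm comparison could detect.** With 60 per arm, one value per paramedic and 80% power: (1.96 + 0.84)·√(2/60) = 0.51 SD. With four segments in a random-intercept model, multiply by √[(1 + 3·ICC)/4]. This gives 0.35 to 0.49 SD for ICC 0.3 to 0.9, before any baseline adjustment.

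**The case against.** The best defence has four parts.

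- **The phases have an order.** Section 2.3.5.1 fixes one chronological progression, so time order is the obvious code. This stands. A reader might infer from the range over all codes that the coefficient is arbitrary and could take either sign. That requires scrambling an order that the protocol fixes. What remains is that the code is unstated and that a time trend does not answer the arm question.
- **Method is not repeated within a person.** Each paramedic uses one method, and r with a two-level variable is a legitimate standardised contrast. This stands, and on the section 2.3.6 reading it would be wrong to say that nothing about the arms is estimated.
- **No section says that readings are pooled, and no HR test or p-value is named.** A reader might infer that the plan carries a type I error of 19% to 29%. The documents do not support that. The figure applies only if HR is correlated with method and four segments per paramedic are treated as independent. On the section 2.3.14.2 reading, arm is not tested at all.
- **HR is peripheral.** Its analysis sits among the additional analyses, and stress is absent from the secondary objective in section 2.3.2. This limits the weight of the point. Even so, the Summary and section 2.3.6 both list measured stress as a secondary outcome.

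**Conclusion.** The point holds as a limited one. The planned correlations do not give the arm difference in bpm for a listed secondary outcome, and the two sections that describe them disagree. Read as correlations within each method, they cannot show a uniform effect of the app; that follows from the algebra and needs no assumed HR values. Read as correlations with method, they are valid with one value per paramedic but unitless. They would be anti-conservative (about 19% to 29% for an assumed ICC of 0.4 to 0.8) only if four segments were pooled as independent.

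The sizes of r depend on assumed HR means and SDs, and the inflation depends on an assumed ICC. The primary analysis, the sample size and the analyses of errors, TDP and TDD are unaffected.

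A reader might also expect a definite precision gain from adjusting for baseline HR instead of using a change score. With equal baseline and segment variances the SE ratio is √[(1 + ρ)/2], where ρ is the correlation of baseline with segment HR: 0.84 at ρ = 0.4 and 0.92 at ρ = 0.7. The documents give neither ρ nor the variances, and equal variances are doubtful for resting against peak HR, so no figure should be promised.

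**What to change.** Change sections 2.3.6 (item D) and 2.3.14.2 together, so that neither keeps the correlation wording:

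- In 2.3.6, define one HR segment per drug sequence and the peak HR within it. Keep the baseline HR already planned.
- In 2.3.14.2, replace the Pearson sentence with: *Peak HR per drug segment will be analysed in a linear mixed model with arm, drug phase, arm by phase and baseline HR as fixed effects and a random intercept for paramedic. The arm difference in bpm will be reported with its 95% CI, overall and by phase.*

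If the sponsor prefers to keep delta HR as the response, the same model with baseline HR as a covariate gives the same arm estimates, so the planned measure is not lost.

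The cost is a short edit in two places. The watch already records the data, and the model family is the one planned for TDP and TDD.
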